13.6 Reporting and Exclusions

Every reasonable attempt will be made to recover any missing data. If any data for the primary efficacy measure remains missing then the change of the primary endpoint for will not be calculated and the participant will not be evaluable for the primary endpoint. However any available data from other time points will be included in the repeated measure analysis.

13.7 Evaluation of Toxicity

All participants will be evaluable for toxicity from the time of their first dose of bexarotene gel. The grade, attribution, onset and resolve date of all toxicities will be recorded and summarized for each dose level at the end of the study.

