Once MTD is identified, we will enroll another 10 participants into MTD and these participants will have mandatory biopsies before and after 4 weeks of treatment. We will continuously monitor aggregate DLTs in these participants together with the 10 participants treated during the dose escalation part of the study. If at any time the posterior probability of observing a DLT rate of at least 20% exceeds 70%, i.e., $\Pr(\text{DLT rate} \geq 0.20 | \text{Data}) > 70\%$, given the prior of the DLT rate of beta (0.2, 0.8), we will stop the trial and claim the dose is too toxic. Given the above rule, the boundaries for early stopping due to excessive DLT are Total Number of Participants with DLTs/Total Number of Participants $\geq 4/11\sim 14$, $5/15\sim 19$, and $6/20$. Combining with the boundaries during dose escalation phase, i.e., stop accrual at the dose level if Total Number of Participants with DLTs/Total Number of Participants $\geq 2/3$, $2/6$, $3/10$, $4/11\sim 14$, $5/15\sim 19$, and $6/20$, the early stopping probability for this level will be 15%, 51%, 82% if the true DLT rate is 0.10, 0.20, and 0.30, respectively.

Given that there are 3 dose levels and 10 participants enrolled at each level, and 10 additional participants at MTD, it is anticipated that 40 participants will be enrolled and treated and up to 40 will be evaluable at the end of this study.

Skin Toxicity

CTCAE criteria will be utilized to grade adverse events. Skin adverse events are expected to be the most common in this study. Bexarotene is similar to retinoids and retinoid dermatitis is very common and can be managed with temporarily withholding drug and restarting at a decreased frequency until tolerated by the individual. Dose modifications for each dose level have been defined in Section 5.5 to guide management of participant experiences of an adverse event

CTCAE criteria for skin will be modified (Table 3) for this study as adverse events are expected to be localized to the breast area. This modified criteria was also utilized by Talpur *et al.* when they evaluated bexarotene 1% gel on the scalp of participants with alopecia areata (6). Please see Table 3 for modified CTCAE criteria. Use plain language when talking to the participant about skin AEs. Refer to Appendix G for a plain language guide to support both phone and in-person assessments of skin application AEs.

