8.3 Off-Agent Criteria

Participants may stop taking study agent for the following reasons: completed the protocol-prescribed intervention, AE or SAE including a DLT, inadequate agent supply, noncompliance, concomitant medications, medical contraindication, or became pregnant. Participants experiencing Grade 3 or Grade 4 toxicities of any attribution will be taken off study drug. Participants will continue to be followed, if possible, for safety reasons and in order to collect endpoint data according to the schedule of events. Participants that receive agent but withdraw without initiating treatment will be replaced and will not be followed or evaluable for DLTs.

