13.3 Accrual and Feasibility

Treatment will be initiated in 10 participants per group up to 40 participants. Participants found eligible but who withdraw without initiating treatment will be replaced and will not be followed or evaluable for DLTs. We plan to screen (consent) 60 participants to enroll (initiate treatment in) up to 40 participants. Our estimated screen out rate after consent prior to study participation is approximately 25%. We anticipate accrual of approx. 3 participants per month. Since accrual is done in groups of 3-4 participants, there will be a 4 week hold in accrual to assess for toxicity in the currently enrolled participants. Assuming that all dose levels are maximally accrued to, there will be 9 months of intentional hold on accrual to assess for safety and toxicity. Therefore, it will take approximately 21 months to complete accrual to the three dose levels and an additional 4 months to accrue to the dose expansion cohort.

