13.4 Primary Objective, Endpoint(s), Analysis Plan

The primary objective of this study is to determine the safety and toxicity of topical 1% bexarotene gel application to the breasts of healthy women at high risk for breast cancer for a duration of 4 weeks. Women with ADH, ALH, LCIS, breast cancer survivors (DCIS or invasive) ≥ 5 years from their diagnosis, BRCA 1/2 mutation carriers, and women with elevated risk for breast cancer $\geq 1.7\%$ in 5 years or lifetime risk $\geq 20\%$ will be recruited. Three dose levels are considered (10mg every other day, 10mg daily, and 20mg daily). Dose Limiting Toxicity (DLT) is defined as a grade 2 skin adverse event that persists for at least 6 days or any grade 3 or greater adverse event possibly, probably, definitely related to the study drug. In addition, a DLT will be a grade 2 skin adverse event that recurs and persists for at least 3 days. A conservative modification of the standard “3+3” design will be applied. The first cohort of 3 participants will be treated at the first dose level (10mg every other day). New cohort of participants will not be treated until toxicity has been fully evaluated for all current participants for 4 weeks. We will add another 4 participants when only 1 or less participants experience DLT in 6 treated participants. We will only escalate dose to the next higher level when 20% or less of total participants experience DLT. At any dose level, the algorithm is as follows:

- (1) If 0 or 1 out of 3 participants experience DLTs ($\leq 1/3$), an additional cohort of 3 participants will be treated at the same dose level. If total number of participants experiencing DLT at that dose level is 1 or less out of 6 ($\leq 1/6$), we will enroll another 4 participants the same dose level.
- (2) If at any time 2 or more participants experiences DLTs in 3 or 6 participants ($\geq 2/3$ or $\geq 2/6$) or 3 or more participants experience DLT in 10 participants ($\geq 3/10$), then the dose escalation will stop, and the next lower dose will be considered as the maximum tolerated dose (MTD).
- (3) In 10 participants at each dose level, if we observe 2 or less DLTs, a cohort of 3 participants will be treated at the next higher level. If 3 or more in 10 participants experience DLT, we will stop accrual to that level and above, and claim the regimen as to be too toxic for that level or above.

MTD is defined the highest dose level with at most 2 participants with DLTs in 10 participants treated.

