Once MTD is identified, we will enroll another 10 participants into MTD and these participants will have mandatory biopsies before and after 4 weeks of treatment. We will continuously monitor aggregate DLTs in these participants together with the 10 participants treated during the dose escalation part of the study. If at any time the posterior probability of observing a DLT rate of at least 20% exceeds 70%, i.e., $\Pr(\text{DLT rate} \geq 0.20 \mid \text{Data}) > 70\%$, given the prior of the DLT rate of beta (0.2, 0.8), we will stop the trial and claim the dose is too toxic. Given the above rule the boundaries for early stopping due to excessive DLT are Total Number of Participants with DLTs/Total Number of Participants $\geq 4/11\sim 14$, $5/15\sim 19$, and $6/20$. Combining with the boundaries during dose escalation phase, i.e., stop accrual at the dose level if Total Number of Participants with DLTs/Total Number of Participants $\geq 2/3$, $2/6$, $3/10$, $4/11\sim 14$, $5/15\sim 19$, and $6/20$, the early stopping probability for this level will be 15%, 51%, 82% if the true DLT rate is 0.10, 0.20, and 0.30, respectively.

Given that there are 3 dose levels and 10 participants enrolled and treated at each level, and 10 additional patients at MTD, it is anticipated that 40 participants will be treated and up to 40 will be evaluable at the end of this study.

At the end of the study, the toxicity data will be summarized for each dose level using frequency tabulation. The compliance of treatment application for each dose level will be presented using descriptive statistics.

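### A woman who starts gel and is lost before 4 weeks counts as DLT-free in the stopping denominator, which slightly biases the expansion 30% rule toward continuing

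*Combined protocol and SAP*

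**What the plan says.** Section 13.7 states: "All participants will be evaluable for toxicity from the time of their first dose of bexarotene gel". Two places say who is not evaluable for DLT, and both concern only women who never apply gel. Section 8.3 has "Participants that receive agent but withdraw without initiating treatment will be replaced and will not be followed or evaluable for DLTs", and Section 13.3 has "Participants found eligible but who withdraw without initiating treatment will be replaced and will not be followed or evaluable for DLTs". For women who stop gel after starting, Section 8.3 adds: "Participants will continue to be followed, if possible, for safety reasons and in order to collect endpoint data according to the schedule of events".

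The pooled boundaries in Section 13.4 are written as "Total Number of Participants with DLTs/Total Number of Participants". The expansion rule in Section 3B ends the trial at 30% or more DLTs among participants, checked after the third and each later woman up to 10.

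A DLT takes time to appear. Under Section 13.4 a Grade 2 skin event counts once it has lasted 6 days, or once it recurs and lasts 3 days. A related event of Grade 3 or higher counts at once. No section sets a minimum observation period before a woman who has started gel is scored DLT-free, and none says whether a starter who is lost is replaced.

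**The concern.** A woman lost after a few applications has not been observed long enough to be called DLT-free at 4 weeks. She still enlarges the denominator and adds nothing to the numerator, so the error runs only toward continuing. The 30% rule works on very small counts from the third woman on, so one such woman can decide the outcome. The participants are healthy women at elevated risk, in whom a missed stop matters. If the team instead leaves her out, it does so after seeing the data and without a rule to point to.

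**Working it through.** **The plan's own figure.** An exact recursion over the boundaries in Section 13.4 (2/3, 2/6, 3/10, 4/11-14, 5/15-19, 6/20) gives stopping probabilities of 15.0%, 51.3% and 82.3% at true DLT rates of 0.10, 0.20 and 0.30. The plan states 15%, 51% and 82%, so it is reproduced. The plan gives no operating characteristics for the 30% rule.

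**The 30% rule without loss.** The smallest DLT count that stops is 1 at n = 3, 2 at n = 4-6 and 3 at n = 7-10. Let p be the true DLT rate, q = 1 - p, and B the number of DLTs among the last four women. The trial continues to the end only with no DLT in the first three, at most one in the fourth to sixth, and at most two in total:

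P(stop) = 1 - q³[q³·P(B ≤ 2) + 3pq²·P(B ≤ 1)].

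At p = 0.3 this is 1 - 0.343 × (0.343 × 0.9163 + 0.441 × 0.6517) = 0.794. At p = 0.1 and 0.2 it is 0.303 and 0.584.

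**Which tallies are reversed.** Adding one DLT-free woman to every stopping tally up to n = 9 reverses only two: 1/3 (33.3%) becomes 1/4 (25.0%), and 2/6 (33.3%) becomes 2/7 (28.6%). For comparison, 3/9 becomes 3/10, which still stops.

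**Chance of a changed decision, given exactly one unobserved leaver among 10.** Compare excluding her with counting her as DLT-free. Order matters: the 1/3 reversal needs her among the first three, with the first DLT in the fourth woman. Probabilities by her position:

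- First to third: pq⁸ + 6p²q⁷ = 0.072, 0.084 and 0.062 at p = 0.1, 0.2 and 0.3.
- Fourth to sixth: 2p²q⁷ = 0.010, 0.017 and 0.015.
- Seventh or later: 0.

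Averaged over the ten positions, (3pq⁸ + 24p²q⁷)/10 = 0.024, 0.030 and 0.023. Enumeration of all 2⁹ outcomes of the other nine women at each position agrees, and finds no change from continue to stop.

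**Stopping probability under assumed loss.** The documents give no loss rate. I take 1/14 (7%) to 20%. The lower figure is the one withdrawal among the 10 + 4 women enrolled at the first two dose levels. If a fraction d is lost, leavers have the same underlying DLT rate and all their DLTs are missed, p becomes p(1 - d). If half are missed, it becomes p(1 - d/2). At p = 0.3:

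- All missed: effective rate 0.279 or 0.240, stopping probability 0.756 or 0.678.
- Half missed: effective rate 0.289 or 0.270, stopping probability 0.775 or 0.740.
- Leavers excluded and not replaced: 0.776 or 0.750.
- Leavers excluded and replaced: 0.794.

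**The pooled rule after 0/10.** It does not make up the difference. Of all 2¹⁰ expansion sequences, none stops under the pooled rule without also stopping under the 30% rule.

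**The case against.** The strongest reply is that the plan already chooses a denominator. Sections 13.7, 8.3 and 13.3 together count everyone who starts, and the MTD is defined per participants treated. That stands, and the criticism is of what this rule does. A reader might go further and infer that the plan supports two competing denominators, but the evidence is thin. In Section 13.4, "it is anticipated that 40 participants will be treated and up to 40 will be evaluable at the end of this study" sets a ceiling that is compatible with all 40 counting. The sentence "New cohort of participants will not be treated until toxicity has been fully evaluated for all current participants for 4 weeks" governs when the next cohort starts. Section 3 locates the second-level DLTs in the remaining patients but states no denominator. Section 13.6 makes a woman with missing data non-evaluable, but it is worded for an efficacy measure.

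It is also fair that stopping gel is not the same as being unobserved. Section 8.3 continues follow-up where possible, and the Day 8 call, the Day 15 and Day 28 visits, the diary and the later call may catch many events. This is why the half-missed range is given beside the worst case. The one reported withdrawal was for unrelated events, and she is not shown to have been unobserved or to have started gel.

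The reversals of 1/3 and 2/6 arise only under Section 3B. Under the pooled rule, after 0/10, those tallies are 1/13 and 2/16, below boundaries of 4 and 5, so the trial would continue in any case. The two expansion rules differ, and that needs reconciling in its own right.

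**Conclusion.** The point holds and is minor. As written, the rule counts an unobserved starter as DLT-free, and the resulting error can only favour continuing. Given one such woman among 10, the decision changes with probability about 2-3%: 6-8% if she is among the first three, 1-2% if fourth to sixth, and none if later. At a true 30% DLT rate, stopping falls from 79% to 76-68% in the worst case, or to 78-74% if half the leavers' DLTs are missed. These ranges rest on assumed losses of 7-20%.

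Two stronger readings are not supported. A reader might infer that the plan's 82% is eroded, but that figure describes a dose level from its first participant. Escalation is complete with 0/10 at the MTD, and from there the pooled rule stops with probability only about 10% at a true 30% rate. A reader might also infer that the MTD is in doubt. The second dose level stops whether its DLTs are counted as 2/3 or 2/4.

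**What to change.** In Sections 8.3, 13.3, 13.4 and 13.7, with the parallel text in 8.1:

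- Define DLT-evaluable as either a DLT at any time after first dose, or a completed 4-week DLT assessment. State that holding or stopping gel for drug-related toxicity never makes a woman non-evaluable.
- Use this denominator for the expansion stopping rule.
- Tally outcomes in enrolment order, or otherwise state how women still under observation are counted. Without this, DLTs enter before DLT-free outcomes. In an illustrative simulation with no loss, 3 women a month, no accrual hold and DLT onset uniform over days 7-28, stopping rose from 30% to about 37% at a true 10% rate, and from 79% to about 84% at 30%.
- Replace non-evaluable starters within the existing ceiling of 40. Escalation used 14 and the expansion plans 10, so 40 - 24 = 16 places remain.
- Keep all treated women in the adverse event tables.
- Report a sensitivity tally that counts lost women as DLTs, for information only. As a boundary it would raise stopping at a true 10% rate from 30% to 49-76%.
- Reconcile the Section 3B rule with the pooled rule in Sections 8.1 and 13.4.

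The cost is a short amendment and possibly one to three replacement women: 10 × d/(1 - d) is 0.8 at 7% loss and 2.5 at 20%. Exclusion without replacement costs no extra women but brings the stopping probability only to 78-75% at a true 30% rate.

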13.8 Evaluation of Response

All participants included in the study must be assessed for response to intervention, even if there are major protocol deviations or if they are ineligible.

All of the participants who met the eligibility criteria (with the possible exception of those who did not receive study agent) will be included in the main analysis. All conclusions regarding secondary efficacy measures requiring breast biopsies will be based on eligible participants selecting this option.

Subanalyses may be performed on the subsets of participants, excluding those for whom major protocol deviations have been identified (e.g., early death due to other reasons, early discontinuation of intervention, major protocol violations, etc.). However, subanalyses may not serve as the basis for drawing conclusions concerning efficacy, and the reasons for excluding participants from the analysis should be clearly reported. For all measurements of response, the 95% confidence intervals should also be provided.

13.9 Interim Analysis

There is continual interim analysis in a modified 3+3 design for this study.

13.10 Ancillary Studies

No additional ancillary studies are planned.

14. ETHICAL AND REGULATORY CONSIDERATIONS

14.1 Form FDA 1572

Prior to initiating this study, the Protocol Lead Investigator at the Lead or Participating Organization(s) will provide a signed Form FDA 1572 stating that the study will be conducted in compliance with regulations for clinical investigations and listing the investigators, at each site that will participate in the protocol. All personnel directly involved in the performance of procedures required by the protocol and the collection of data should be listed on Form FDA 1572.

14.2 Other Required Documents

14.2.1 Current (within two years) CV or biosketch for all study personnel listed on the Form FDA 1572 and Delegation of Tasks form for the Lead Organization and all Participating Organizations.

14.2.2 Current medical licenses (where applicable) for all study personnel listed on Form FDA 1572 and Delegation of Tasks form for the Lead Organization and all Participating Organizations.

14.2.3 Lab certification (*e.g.*, CLIA, CAP) and lab normal ranges for all labs listed on Form FDA 1572 for the Lead Organization and all Participating Organizations.

14.2.4 Documentation of training in “Protection of Human Research Subjects” for all study personnel listed on the FDA Form 1572 and Delegation of Tasks form for the Lead Organization and all Participating Organizations.

14.2.5 Documentation of Federalwide Assurance (FWA) number for the Lead Organization and all Participating Organizations.

14.2.6 Signed Investigator’s Brochure/Package Insert acknowledgement form

14.2.7 Delegation of Tasks form for the Lead Organization and all Participating Organizations signed by the Principal Investigator for each site and initialed by all study personnel listed on the form

14.2.8 Signed and dated NCI, DCP Financial Disclosure Form for all study personnel listed on Form FDA 1572 for the Lead Organization and all Participating Organizations

14.3 Institutional Review Board Approval

Prior to initiating the study and receiving agent, the Investigators at the Lead Organization and the Participating Organization(s) must obtain written approval to conduct the study from the appropriate IRB. Should changes to the study become necessary, protocol amendments will be submitted to the DCP PIO according to DCP Amendment Guidelines. The DCP-approved amended protocol must be approved by the IRB prior to implementation

14.4 Informed Consent

All potential study participants will be given a copy of the IRB-approved Informed Consent to review. The investigator will explain all aspects of the study in lay language and answer all questions regarding the study. If the participant decides to participate in the study, he/she will be asked to sign and date the Informed Consent document. The study agent(s) will not be released to a participant who has not signed the Informed Consent document. Subjects who refuse to participate or who withdraw from the study will be treated without prejudice.

Participants must be provided the option to allow the use of blood samples, other body fluids, and tissues obtained during testing, operative procedures, or other standard medical practices for further research purposes. If applicable, statement of this option may be included within the informed consent document or may be provided as an addendum to the consent. A Model Consent Form for Use of Tissue for Research is available through a link in the DCP website.

Prior to study initiation, the informed consent document must be reviewed and approved by NCI, DCP, the Consortium Lead Organization, and the IRB at each Organization at which the protocol will be implemented.

Any subsequent changes to the informed consent must be approved by NCI, DCP, the Consortium Lead Organization's IRB, and then submitted to each organization's IRB for approval prior to initiation.

14.6 Other

This trial will be conducted in compliance with the protocol, Good Clinical Practice (GCP), and the applicable regulatory requirements.

APPENDIX A
Performance Status Criteria

ECOG Performance Status Scale

Grade	Descriptions
0	Normal activity. Fully active, able to carry on all pre-disease performance without restriction.
1	Symptoms, but ambulatory. Restricted in physically strenuous activity, but ambulatory and able to carry out work of a light or sedentary nature (e.g., light housework, office work).
2	In bed <50% of the time. Ambulatory and capable of all self-care, but unable to carry out any work activities. Up and about more than 50% of waking hours.
3	In bed >50% of the time. Capable of only limited self-care, confined to bed or chair more than 50% of waking hours.
4	100% bedridden. Completely disabled. Cannot carry on any self-care. Totally confined to bed or chair.
5	Dead.

[figure not shown]
Karnofsky Performance Scale

Percent	Description
100	Normal, no complaints, no evidence of disease.
90	Able to carry on normal activity; minor signs or symptoms of disease.
80	Normal activity with effort; some signs or symptoms of disease.
70	Cares for self, unable to carry on normal activity or to do active work.
60	Requires occasional assistance, but is able to care for most of his/her needs.
50	Requires considerable assistance and frequent medical care.
40	Disabled, requires special care and assistance.
30	Severely disabled, hospitalization indicated. Death not imminent.
20	Very sick, hospitalization indicated. Death not imminent.
10	Moribund, fatal processes progressing rapidly.
0	Dead.

